## 7.3. Exploratory Efficacy Analyses

### 7.3.1. Population of Interest

The population of interest is represented by the randomization inclusion/exclusion criteria of the study and therefore the exploratory efficacy analyses will be based on the Intent-to-Treat (ITT) [Part C] population, unless otherwise specified.

### 7.3.2. Statistical Analyses / Methods

Details of the planned displays are provided in [Appendix 11: List of Data Displays](#) and will be based on GSK data standards and statistical principles.

#### 7.3.2.1. Statistical Methodology Specification

Endpoint / Variables

 
• Time to first exacerbation requiring hospitalization (ADaM Dataset: ADTTE)
 
• Time to worsening of asthma (subjects meeting at least 2 of the following 4 criteria for worsening of asthma for at least 2 consecutive days) (ADaM Dataset: ADTTE):               
 
○ AM PEF: Decrease in AM PEF <math>\geq 30\%</math> compared with Part C baseline
 
○ Rescue Medication Use: An increase of <math>\geq 50\%</math> in rescue medication compared with the average use for the previous week
 
○ Night time awakenings requiring rescue medication: Awakening due to asthma symptoms requiring rescue medication
 
○ Symptoms: An asthma symptom score of 5
 
 
 

 
• Time to first event within Part C will be derived relative to the date of first dose of double-blind treatment [see Section 11.6.1, Part C study day].
 
• For consistency, exacerbations separated by less than 7 days will be treated as a continuation of the same exacerbation (see Section 11.6.3).
 
• See Section 5.2 for further details regarding baseline and change from baseline derivations.
 
• See Section 11.6.3 for details regarding eDiary data and Section 11.3.5 regarding visit windowing.
 
• In the analysis of Time to worsening of asthma only non-missing measurements indicative of asthma worsening (per above endpoint definition) will be considered as an event. Intermediate missing responses in a subject's eDiary data will be assumed to be missing at random, and will not be considered to indicate a worsening of their asthma.
 
• See Section 11.7.2 for further details on handling missing/partial data.
 

Summary Measure

 
• The hazard ratio (Mepolizumab 100mg SC / Placebo) will be the summary measure used for the treatment comparison.
 

Strategy for Intercurrent (Post-Randomization) Events

 
• A hypothetical estimand strategy will be applied in the handling of the intercurrent event of discontinuation of double-blind treatment. The treatment effect therefore refers to the outcome if all patients had continued to take double-blind treatment.
 
• Only the On-treatment (Part C) period will be used in the analysis and subjects will be analysed according to the treatment received for more than 50% of injections within Part C (see Section 5.1).
 
• All subjects will be considered to be at risk from their first dose of double-blind treatment at visit C1. Subjects who complete Part C will be considered to be at risk up to their Week 52 (Exit Visit/C14) visit date. Subjects who discontinued double-blind treatment prior to experiencing an event will be censored at the time of treatment discontinuation.               
 
○ Exacerbations: see On-treatment (Part C) definition within Section 11.4.2
 
○ eDiary data: see On-treatment (Part C) definition within Section 11.4.3.
 
 
 

Model Specification

 
See Primary Efficacy Statistical Analysis, Section 7.1.5.1
 

Model Checking & Diagnostics

 
See Primary Efficacy Statistical Analysis, Section 7.1.5.1
 

Model Results Presentation

 
See Primary Efficacy Statistical Analysis, Section 7.1.5.1
 

Endpoint / Variables

 
Mean change from baseline in clinic pre-bronchodilator FEV1 at weeks 12, 24, 36, 52
 
Mean change from baseline in clinic post-bronchodilator FEV1 at weeks 12, 24, 36, 52 (ADaM Dataset: ADPFT)
 
Mean change from baseline in ACQ-5 score (ADaM Dataset: ADACQ5)
 
Mean change from baseline in SGRQ Total score at week 12, 24, 36 and 52
 
Mean change from baseline in SGRQ Symptom Domain score at week 12, 24, 36 and 52
 
Mean change from baseline in SGRQ Activity Domain score at week 12, 24, 36 and 52
 
Mean change from baseline in SGRQ Impacts Domain score at week 12, 24, 36 and 52 (ADaM Dataset: ADSGRQ)
 


 
See Section 5.2 for further details regarding baseline and change from baseline derivations.
 
See Section 11.6.3 for additional details regarding spirometry, the ACQ-5 and SGRQ questionnaires.
 
See Section 11.3.5 regarding visit windowing of the ACQ-5 questionnaire.
 

Summary Measure

 
Spirometry and SGRQ: Mean treatment difference at weeks 12, 24, 36 and 52 (Exit Visit/C14)
 
ACQ-5: Mean treatment difference at weeks 12, 24, 36 and 52
 

Strategy for Intercurrent (Post-Randomization) Events

 
A hypothetical estimand strategy will be applied in the handling of the intercurrent event of discontinuation of double-blind treatment. The treatment effect therefore refers to the outcome if all patients had continued to take double-blind treatment.
 
Only the On-treatment (Part C) period will be used in the analysis and subjects will be analysed according to the treatment received for more than 50% of injections within Part C (see Section 5.1).
 
All subjects will be considered on-treatment from their first dose of double-blind treatment at visit C1. Subjects who complete Part C will be considered on-treatment up to their Week 52 (Exit Visit/C14) visit date. Subjects who discontinued double-blind treatment will be considered on-treatment until the time of treatment discontinuation. 
 
Spirometry and Questionnaires: see On-treatment (Part C) definition within Section 11.4.3
 
 
 

Model Specification

 
See Secondary Efficacy Statistical Analysis, Section 7.2.2.1.
 

Model Checking & Diagnostics

 
See Secondary Efficacy Statistical Analysis, Section 7.2.2.1.
 

Model Results Presentation

 
The estimated means for each treatment group will be calculated from the model using the observed marginal distributions of the sample covariates (OM option in LSMEANS statement).
 
Adjusted absolute means and mean changes from baseline will be presented for each treatment by visit with corresponding standard errors of means. The estimated treatment difference (Mepolizumab – Placebo) will also be presented at each visit with the corresponding 95% confidence intervals and p-values.
 
Plots of LS means change from baseline and 95% confidence intervals from the model will be generated for each treatment by visit.
 

Endpoint / Variables

 
Proportion of patients experiencing a decrease in asthma control, defined as an increase from baseline in ACQ-5 score of <math>\geq 0.5</math> units (ADaM Dataset: ADACQ5)
 
Proportion of subjects with a clinically meaningful worsening of health-related quality of life measurements (SGRQ) at weeks 12, 24, 36 and 52 (defined as subjects who have a clinically relevant increase from baseline of <math>\geq 4</math> units in SGRQ total score) (ADaM Dataset: ADSGRQ)
 

 
See Section 5.2 for further details regarding baseline and change from baseline derivations.
 
See Section 11.6.3 for additional details regarding the ACQ-5 and SGRQ questionnaires.
 
See Section 11.3.5 regarding visit windowing of the ACQ-5 questionnaire.
 

Summary Measure

 
ACQ-5: Odds Ratio (Mepolizumab 100mg SC / Placebo) at weeks 12, 24, 36 and 52
 
SGRQ: Odds Ratio (Mepolizumab 100mg SC / Placebo) at weeks 12, 24, 36 and 52 (Exit Visit/C14)
 

Strategy for Intercurrent (Post-Randomization) Events

 
A composite estimand strategy will be applied in the handling of the intercurrent event of discontinuation of double-blind treatment.
 
Subjects will be categorized during the On-treatment (Part C) period according to their questionnaire (ACQ-5 / SGRQ) response. Following treatment discontinuation (end of On-treatment [Part C] phase) subjects will be shown as missing and on analysis included in the least favorable category of increase from baseline of <math>\geq 0.5</math> units or <math>\geq 4</math> units for the ACQ-5 and SGRQ endpoints, respectively.
 
Subjects will be analysed according to the treatment received for more than 50% of injections within Part C (see Section 5.1).
 
All subjects will be considered on-treatment from their first dose of double-blind treatment at visit C1. Subjects who complete Part C will be considered on-treatment up to their Week 52 (Exit Visit/C14) visit date. Subjects who discontinued double-blind treatment will be considered on-treatment until the time of treatment discontinuation. 
 
Questionnaires: see On-treatment (Part C) definition within Section 11.4.3
 
 
 

Model Specification

 
Logistic regression will be used to compare the proportion of patients achieving a 0.5 units / 4 point or greater increase from baseline in ACQ-5 / SGRQ Total Score between treatment groups at each analysis visit (separate models will be used for each analysis visit).
 
Subjects with a missing response at a particular visit will be included in the least favorable category as having a 0.5 units / 4 point or greater increase from baseline in ACQ-5 / SGRQ Total Score in the logistic regression model for the analysis of that visit.
 
Terms fitted in each logistic regression model will include: 
 
Fixed Categorical Covariates: Treatment, Region, Baseline maintenance OCS use [Visit C1]
 
Fixed Continuous Covariates: Baseline Score, Exacerbations in the year prior to randomization [Visit C1] (as an ordinal variable)
 
 
 
 
See Section 5.4.1 for further details around model covariates.

Model Checking & Diagnostics

 
In the event that this model fails to converge, the list of covariates may be adjusted and/or reduced.
 
Distributional assumptions underlying the model used for analysis will be examined by: 
 
assessing if a sufficient number of events occurred within covariate categories.
 
 
 
If there are any major important departures from the distributional assumptions transformations of covariates may be considered or alternative models may be explored as supportive analysis.
 

Model Results Presentation

 
The number and percentage of subjects achieving a 0.5 units / 4 point or greater increase in ACQ-5 / SGRQ Total Score compared to baseline will be presented by treatment group for each visit.
 
The estimated odds ratio (Mepolizumab/Placebo) at each visit for the treatment variable in the logistic regression model will be reported with the corresponding 95% CI and p-value.
 

Endpoint / Variables

 
Subject/Clinician global impression of asthma severity rating at weeks 12, 24, 36 and 52 (ADaM Dataset: ADGLOBRT)
 
Subject/Clinician rating of response to therapy at weeks 12, 24, 36 and 52 (ADaM Dataset: ADEVRESP)
 

 
See Section 5.2 for further details regarding baseline derivations.
 
See Section 11.6.3 for additional details regarding the Subject/Clinician global impression of asthma severity rating and the Subject/Clinician rating of response to therapy questionnaires.
 

Summary Measure

 
Subject/Clinician global impression of asthma severity rating: Odds Ratio (Mepolizumab 100mg SC / Placebo) at weeks 12, 24, 36 and 52 (Exit Visit/C14)
 
Subject/Clinician rating of response to therapy: Odds Ratio (Mepolizumab 100mg SC / Placebo) at weeks 12, 24, 36 and 52 (Exit Visit/C14)
 

Strategy for Intercurrent (Post-Randomization) Events

 
A composite estimand strategy will be applied in the handling of the intercurrent event of discontinuation of double-blind treatment.
 
Subjects will be categorized during the On-treatment (Part C) period according to their response. Following treatment discontinuation (end of On-treatment [Part C] phase) subjects will be shown as missing and on analysis included in the least favorable category of the respective outcome.
 
Subjects will be analysed according to the treatment received for more than 50% of injections within Part C (see Section 5.1).
 
All subjects will be considered on-treatment from their first dose of double-blind treatment at visit C1. Subjects who complete Part C will be considered on-treatment up to their Week 52 (Exit Visit/C14) visit date. Subjects who discontinued double-blind treatment will be considered on-treatment until the time of treatment discontinuation. 
 
Questionnaires: see On-treatment (Part C) definition within Section 11.4.3
 
 
 

Model Specification

 
Ordinal logistic regression (proportional odds model) will be used to compare the proportion of patients in each response category between treatment groups at each analysis visit (separate models will be used for each analysis visit).
 
Subjects with a missing response at a particular visit will be included in the least favorable category of the respective outcome in the ordinal logistic regression model for the analysis of that visit.
 
Terms fitted in each ordinal logistic regression model will include: 
 
Fixed Categorical Covariates: Treatment, Baseline (Global impression of asthma severity rating only), Region, Baseline maintenance OCS use [Visit C1]
 
Fixed Continuous Covariates: Exacerbations in the year prior to randomization [Visit C1] (as an ordinal variable)
 
 
 
 
See Section 5.4.1 for further details around model covariates.

Model Checking & Diagnostics

 
In the event that this model fails to converge, the list of covariates may be adjusted and/or reduced.
 
Distributional assumptions underlying the model used for analysis will be examined by: 
 
assessing if a sufficient number of events occurred within covariate categories.
 
 
 
If there are any major important departures from the distributional assumptions transformations of covariates may be considered or alternative models may be explored as supportive analysis.
 

Model Results Presentation

 
The number and percentage of subjects in each response category and with a missing response will be presented by treatment group for each visit.
 
The estimated odds ratio (Mepolizumab/Placebo) at each visit for the treatment variable in the ordinal logistic regression model will be reported with the corresponding 95% CI and p-value.
 

### 7.3.3. Change from Baseline in eDiary Parameters

Daily eDiary data for the following parameters will be aggregated whilst on-treatment over 4-weekly periods (see Section 11.3.5) within study Part C, respectively:

- Occasions/day of rescue medication (salbutamol/albuterol) usage over the previous 24-hours
- Asthma symptom score over the previous 24-hours (using a 6-point scale)
- Frequency of awakening due to asthma symptoms requiring rescue medication use
- Morning peak expiratory flow [PEF] (L/min), before rescue medication usage

The mean daily data whilst on-treatment, excluding days with missing data, will be calculated for each 4-weekly period (Weeks 0-4, 4-8, ..., 48-52) within study Part C, respectively. Data for each 4-week period and change from baseline for each 4-week period will be summarised by treatment group.

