### 2.3.3. Other Endpoints

- Time to first exacerbation requiring hospitalization
- Mean change from baseline in clinic pre-bronchodilator FEV1 at weeks 12, 24, 36, 52
- Mean change from baseline in clinic post-bronchodilator FEV1 at weeks 12, 24, 36, 52
- Mean change from baseline in daily salbutamol/albuterol use (occasions/day)
- Mean change from baseline in daily asthma symptom scores
- Mean change from baseline in awakening at night due to asthma symptoms requiring rescue medication use
- Mean change from baseline in morning (AM) Peak Expiratory Flow (PEF)
- Time to worsening of asthma (subjects meeting at least 2 of the following 4 criteria for worsening of asthma for at least 2 consecutive days)
  - **AM PEF:** Decrease in AM PEF  $\geq 30\%$  compared with baseline
  - **Rescue Medication Use:** An increase of  $\geq 50\%$  in rescue medication compared with the average use for the previous week
  - **Night time awakenings requiring rescue medication:** Awakening due to asthma symptoms requiring rescue medication
  - **Symptoms:** An asthma symptom score of 5
- Mean change from baseline in ACQ-5 score

- Proportion of patients experiencing a decrease in asthma control, defined as an increase from baseline in ACQ-5 score of  $\geq 0.5$  units
- Proportion of subjects with a clinically meaningful worsening of health-related quality of life measurements (SGRQ) at weeks 12, 24, 36 and 52 (defined as subjects who have a clinically relevant increase from baseline of  $\geq 4$  units in SGRQ score).
- Mean change from baseline in SGRQ Total score at week 12, 24, 36 and 52
- Subject/Clinician global impression of asthma severity rating at weeks 12, 24, 36 and 52
- Subject/Clinician rating of response to therapy at weeks 12, 24, 36 and 52
- Number of days in hospital due to asthma
- Unscheduled healthcare contacts/resource utilization
- Days off of regular work/school

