#### 7.2.2.1. Statistical Methodology Specification

Endpoint / Variables

 
Ratio to baseline in blood eosinophil count at weeks 12, 24, 36 and 52 (ADaM Dataset: ADLB)
 
See Section 5.2 for further details regarding baseline and change from baseline derivations.
 
See Section 11.6.3 for additional details regarding handling blood eosinophil data.
 

Summary Measure

 
Mean treatment difference at weeks 12, 24, 36 and 52 (Exit Visit/C14)
 

Strategy for Intercurrent (Post-Randomization) Events

 
A hypothetical estimand strategy will be applied in the handling of the intercurrent event of discontinuation of double-blind treatment. The treatment effect therefore refers to the outcome if all patients had continued to take double-blind treatment.
 
Only the On-treatment (Part C) period will be used in the analysis and subjects will be analysed according to the treatment received for more than 50% of injections within Part C (see Section 5.1).
 
All subjects will be considered on-treatment from their first dose of double-blind treatment at visit C1. Subjects who complete Part C will be considered on-treatment up to their Week 52 (Exit Visit/C14) visit date. Subjects who discontinued double-blind treatment will be considered on-treatment until the time of treatment discontinuation. 
 
Blood Eosinophils: see On-treatment (Part C) definition within Section 11.4.3
 
 
 

Model Specification

 
Endpoint will be analysed using a mixed model repeated measures (MMRM) model
 
A log transformation will be applied to blood eosinophil count data prior to analysis.
 
Terms fitted in the MMRM model will include: 
 
Fixed Categorical Covariates: Treatment, Region, Baseline maintenance OCS use [Visit C1], Visit, Visit * Treatment Interaction
 
Fixed Continuous Covariates: Baseline, Exacerbations in the year prior to randomization [Visit C1] (as an ordinal variable), Visit * Baseline
 
Repeated: Visit
 
 
 
See Section 5.4.1 for further details around model covariates.
 

Model Checking & Diagnostics

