2.36.	ITT (Part C)	SHELL	Summary and Analysis of Subject Global Impression of Asthma Severity Rating (Part C)		SAC
2.37.	ITT (Part C)	SHELL	Summary of Shift From Baseline in Subject Global Impression of Asthma Severity Rating (Part C)		SAC
2.38.	ITT (Part C)	SHELL	Summary and Analysis of Clinician Global Impression of Asthma Severity Rating (Part C)		SAC
2.39.	ITT (Part C)	SHELL	Summary of Shift From Baseline in Clinician Global Impression of Asthma Severity Rating (Part C)		SAC

Efficacy: Tables					
No.	Population	IDSL / Example Shell	Title	Programming Notes	Deliverable [Priority]
Rating of Response to Therapy					
2.40.	ITT (Part C)	SHELL	Summary and Analysis of Subject Rated Overall Evaluation of Response to Therapy (Part C)		SAC
2.41.	ITT (Part C)	SHELL	Summary and Analysis of Clinician Rated Overall Evaluation of Response to Therapy (Part C)		SAC
eDiary Parameters					
2.42.	ITT (Part C)	SHELL	Summary of Daily Salbutamol/Albuterol Use (occasions/day) by 4-Week Period (Part C)		SAC
2.43.	ITT (Part C)	SHELL	Summary of Daily Asthma Symptom Scores by 4-Week Period (Part C)		SAC
2.44.	ITT (Part C)	SHELL	Summary of Awakening at Night Due to Asthma Symptoms Requiring Rescue Medication Use by 4-Week Period (Part C)		SAC
2.45.	ITT (Part C)	SHELL	Summary of Morning Peak Expiratory Flow (PEF) by 4-Week Period (L/min) (Part C)		SAC
2.46.	ITT (Part C)	SHELL	Analysis of Time to First Worsening of Asthma Defined by Daily eDiary Parameters (Part C)	Footnote: Subjects meeting at least 2 of the possible 4 criteria for worsening of asthma for at least 2 consecutive days	SAC
Number of Days in Hospital Due to Asthma					
2.47.	ITT (Part C)	SHELL	Summary of Days in Hospital Due to Asthma Symptoms (Part C)		SAC
Unscheduled Healthcare Contacts/Resource Utilization					
2.48.	ITT (Part C)	SHELL	Summary of Unscheduled Healthcare Resource Use (Part C)	Separate pages for: 1) use associated with an exacerbation 2) use not associated with an exacerbation, 3) total resource use	SAC
Number of Days off Work/School					
2.49.	ITT (Part C)	SHELL	Summary of Days Off Work/School Due to Asthma Symptoms (Part C)		SAC

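### The four eDiary mean-change endpoints get only raw on-treatment means by arm, with no between-arm estimate, and the late-period means describe a group probably selected differently by arm

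*SAP*

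**What the plan says.** SAP 2.3.3 lists the four eDiary parameters as mean change from baseline, in the same form as FEV1, ACQ-5 and SGRQ. SAP 7.3.3 then builds period averages: "The mean daily data whilst on-treatment, excluding days with missing data, will be calculated for each 4-weekly period". There are 13 such periods (SAP 11.3.5). The reporting rule is: "Data for each 4-week period and change from baseline for each 4-week period will be summarised by treatment group". In the list of displays (SAP 11.11.5.3), Tables 2.42 to 2.45 are all summaries, and no figure is planned for these means.

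For FEV1, ACQ-5 and SGRQ, SAP 7.3.2.1 states a hypothetical strategy, "The treatment effect therefore refers to the outcome if all patients had continued to take double-blind treatment", and refers to the model in SAP 7.2.2.1: "Endpoint will be analysed using a mixed model repeated measures (MMRM) model". Adjusted differences with 95% intervals and p-values follow at each visit.

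Diary data count as on-treatment up to the first Part D dose for switchers. For other discontinuers the limit is the earlier of 28 days after the last double-blind dose and the withdrawal or discontinuation visit (SAP 11.4.3). Later data are left out (protocol 10.4.2), although diary entry continues in Part D and after treatment is stopped (protocol 6.6, 8.3.2.2).

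**The concern.** The eDiary endpoints have the same form and the same route out of the analysis as ACQ-5, which comes from the same device in the same subjects. ACQ-5 gets a model and a stated estimand, and the diary means get neither. A reader will place raw arm means beside modelled FEV1 and ACQ-5 differences with no interval to judge them by.

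The raw means also change population over time. The protocol expects heavy loss from Part C (5.4), largely through a switch that follows an exacerbation, and more exacerbations on placebo. If those who leave were doing worse on the diary, the placebo means in late periods will look better than they should.

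SAP 11.7.2 assumes missing diary responses are missing at random and concludes that only non-missing values need summarising. That assumption does not in general justify raw observed means; it is the assumption under which a likelihood-based repeated-measures model is valid. The sentence concerns missed entries, but nothing else is said about drop-out for these endpoints. The next section, SAP 7.3.4, does split its summaries by weeks of treatment completed.

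**Working it through.** **1. The plan's own figures.** Inputs from protocol 10.2.1: 150 per arm, 40% and 60.5% with an exacerbation, 20% withdrawing first.

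- Hazard ratio = ln(1 − 0.40) / ln(1 − 0.605) = 0.550, as stated. With 52.5% on placebo it is 0.686, as stated.
- Events = 150 × (0.40 + 0.605) × 0.8 = 120.6.
- Power = Φ(|ln 0.55| × √(120.6/4) − 1.96) = 90.7%, against 90% stated.
- Disposition: 120.6 exacerbators, 60 withdrawals and 119.4 event-free, against about 120 exacerbators and about 120 Part C completers in protocol 5.3.

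The planning figure for completers therefore corresponds to nearly all exacerbators leaving Part C.

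**2. Who remains at Week 52.** Let s be the share of exacerbators who switch. Remaining per arm = 150 − 30 − s × 150 × p × 0.8, with p = 0.40 or 0.605. The documents do not give s, so it is varied.

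| s | Mepolizumab on treatment (of whom exacerbated) | Placebo on treatment (of whom exacerbated) |
|---|---|---|
| 0.25 | 108.0, 72% (33%) | 101.8, 68% (54%) |
| 0.50 | 96.0, 64% (25%) | 83.7, 56% (43%) |
| 0.75 | 84.0, 56% (14%) | 65.5, 44% (28%) |
| 1.00 | 72.0, 48% (0%) | 47.4, 32% (0%) |

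This takes withdrawal as equal in both arms and assumes that exacerbators who stay remain to the end.

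**3. What this could do to the means.** Three simulations in SD units used the 40% and 60.5% event proportions and 20% withdrawal. The true difference and the link between diary worsening and exacerbation are assumptions.

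- *Longitudinal, 25 trials per scenario:* 13 periods, individual drifts, exacerbation hazard rising with individual worsening, true late difference 0.50. If all exacerbators switch, raw means give 0.40–0.41 and a likelihood-based repeated-measures estimate 0.47–0.49. If 60% switch, raw means give 0.48–0.49 and the model 0.49–0.51.
- *Same design, separate code, 60 trials per scenario:* under full switching, raw 0.37–0.43 (14 to 26% too small, since 0.07/0.50 = 14% and 0.13/0.50 = 26%) and model 0.44–0.48. At 60% switching, 0.49–0.51 for both.
- *Single late period, 400,000 subjects per arm, true placebo worsening 0.30, mepolizumab 0, withdrawal at random.* The table shows the observed placebo mean and the arm difference, by correlation between exacerbation and diary worsening:

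| Correlation | s = 1: placebo; difference | s = 0.5: placebo; difference |
|---|---|---|
| 0 | 0.31; 0.31 | 0.30; 0.30 |
| 0.2 | 0.11; 0.23 | 0.24; 0.29 |
| 0.4 | −0.09; 0.17 | 0.19; 0.29 |
| 0.6 | −0.29; 0.10 | 0.13; 0.28 |

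With no link there is no bias. With half switching, the placebo mean is flattered but so is the mepolizumab mean, and the difference loses only 3 to 8% (0.291 and 0.277 against 0.30). With full switching the loss is 23 to 66% (0.231 and 0.102 against 0.30). With a true difference of 0.50 the same set-up gives 0.44, 0.37 and 0.30 under full switching.

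**The case against.** Three stronger readings are tempting, and the documents support none of them.

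- *Late periods compare only subjects who did not exacerbate.* An exacerbation does not end on-treatment data. The investigator decides whether the subject continues (protocol 5.1) and the switch is optional (protocol Table 3). Exacerbators who stay in Part C contribute to every later mean. The reading is exact only if all of them leave; the planning figures come close to that, but they are expectations, not a rule.
- *The placebo decline is understated, as a fact.* No figure in the documents links diary values to leaving. Each simulation builds that link in.
- *Any discordance with FEV1 or ACQ-5 would be purely methodological.* Nothing establishes this, and the endpoints could differ for real reasons.

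Monte Carlo error also matters. With unit SD and about 47% and 33% of 150 remaining, one trial's SE is √(1/70.5 + 1/49.5) ≈ 0.19, so a 25-trial mean has an SE of about 0.037. The 60% results cannot be told from no bias.

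Part of the gap is covered elsewhere. Table 2.46 models time to worsening of asthma from the same four parameters, with a hazard ratio, interval and p-value. ACQ-5, which asks about night waking and symptoms, gets a repeated-measures model. SAP 6.2 shows attrition by a Kaplan-Meier plot and by attendance at each visit. These are other endpoints without multiplicity adjustment, whose methods the protocol left to the SAP, and a descriptive table is a legitimate choice.

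All of this stands against certainty and size. It does not supply a mean-change estimate: Table 2.46 estimates time to an event, and the four listed endpoints still have no between-arm difference, interval or stated strategy.

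**Conclusion.** The gap is certain: four mean-change endpoints are reported only as raw on-treatment means by arm, without the model, between-arm estimate or intercurrent-event strategy given to the comparable endpoints. That late-period means describe a group selected differently by arm is probable, from the protocol's own event and withdrawal inputs. That this understates the placebo worsening is probable only if leavers have worse diary values than stayers.

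The longitudinal simulations suggest an arm difference about 15 to 25% too small under full switching, and the single-period calculation suggests more if the link is strong. At 50 to 60% switching the effect on the difference is small in all three. These sizes rest on assumed drifts, correlations and switch shares and cannot be derived from the documents. The case for a change does not depend on the bias, since the missing estimate and interval are reason enough. It is a low-priority improvement and leaves the primary result untouched.

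**What to change.** Before unblinding, add to SAP 7.3.3 a repeated-measures model for the 4-weekly change from baseline in each parameter, with the SAP 7.2.2.1 terms: treatment, region, maintenance OCS use, prior-year exacerbations, baseline, period, period by treatment and period by baseline. Use the same hypothetical strategy and state that it relies on missing at random. In the simulations the model reduced the bias without always removing it.

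Pre-state two things:

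- *Covariance.* Thirteen periods under an unstructured matrix need 13 × 14 / 2 = 91 parameters per endpoint, and the only convergence fallback in SAP 7.2.2.1 is to change the covariates. Name a structured alternative and when it applies.
- *Skewness.* Rescue use and awakenings are likely to be skewed. Choose on blinded data between, for example, a transformed scale and a bootstrap interval. The simulations assumed normality and do not test this.

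Report the adjusted difference and 95% interval for the periods ending at Weeks 12, 24, 36 and 52, to match the other endpoints. This gives 4 × 4 = 16 contrasts instead of 4 × 13 = 52. Show n per period and arm, and keep the raw summaries as description.

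The cost is four extra exploratory models using a specification the SAP already contains, plus unadjusted contrasts that should be labelled as such. No new data are needed.
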